There is a growing body of evidence to suggest that a combination of multiple hemodynamic and inflammatory factors contribute to this elevated risk. These factors operate simultaneously and sequentially, contributing to the poor outcomes. They include the repetitive hemodynamic insult precipitated by rapid volume removal with HD and the immune dysregulation accentuated by dialysis. It has been shown that dialysis is associated with a repetitive ischemic injury termed myocardial stunning (MS)³. A subsequent observational study over 12 months has shown that MS is associated with 30% mortality and 10% reduction in left ventricular ejection fraction⁴. Larger inter-dialytic weight gain (IDWG) with the requirement for larger ultrafiltration volume is strongly associated with MS and increased mortality⁴⁻⁶, specifically for ultrafiltration (UF) requirements exceeding 12.37 ml/h/kg. It seems that HD itself may contribute to the development of heart failure and the risk of sudden death. In addition to the hemodynamic instability precipitated by HD, these patients are subject to substantive metabolic and inflammatory stress⁷.

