6.3.15 Dialysis Prescription

- ❖ Subjects will have their routine hemodialysis treatment with the added SCD filter.
- ❖ All “chronic hemodialysis treatments” will be conducted according to usual clinical practice, using standard hemodialysis machines.
- ❖ The schedule of chronic dialysis will be consistent with the research subjects’ routine treatment day.

- ❖ The Principal Investigator will adjust net ultrafiltration to achieve the patient's established stable dry weight.

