8.5 Study Exit Procedures

A Study Termination form will be completed for all patients who have completed the Study Procedures according to the protocol as well as for those who are terminating early for any cause

9. Statistical Considerations

Sample size determination for primary outcome regional wall abnormalities: Our consultant, [name] has previously demonstrated a difference in this variable in 8 to 10 patients using a similar protocol to this proposal when comparing standard and biofeedback dialysis and dialysis cooling ^{33,34}. Sample size of 10 would appear to be sufficient to detect a difference of 20% and is based upon a standard deviation of 14%, significance level of 0.05 and 80% power. In the [name] studies, differences of greater than 20% were observed. We plan to recruit 10 patients in this study, to better ensure an adequate sample size to obtain statistically relevant primary and secondary endpoint comparisons. The patients will serve as their own controls, comparing BL-SHH parameters to SCD therapy parameters. Independent t-test will be used to compare the peak frequency of MS between SHH and SCD sessions. Global LVEF and wall motion in 16 segments in 8 regions at each time point in the dialysis session will be compared using repeated measures and Bonferroni's test for multiple comparisons. IDWG will be compared using paired and unpaired non-parametric testing or t-test if the variable is

normally distributed. These approaches have shown significance in prior studies for MS in HD. Statistical correlations are planned for regional wall abnormalities, inflammatory indices, monocyte subsets and pre-dialysis blood pressures ^{33,34}

10. Adverse Events

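### Net ultrafiltration can differ between the two fixed-order sessions, yet Section 9 only compares IDWG, partly with unpaired tests, and adjusts no outcome for it

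*Combined protocol and SAP*

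**What the plan says.** Section 1 (Background and Rationale) states that "Larger inter-dialytic weight gain (IDWG) with the requirement for larger ultrafiltration volume is strongly associated with MS" and cites a UF requirement above 12.37 ml/h/kg. Its subsection on stunning also names high UF rates as associated with stunning.

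UF follows the weight of the day. Section 6.3.15 says "The Principal Investigator will adjust net ultrafiltration to achieve" the patient's dry weight. Section 6.3.4, step 3, computes hourly net UF as pre-dialysis weight minus dry weight, times 1000, divided by 4 hours. Section 8.3.1 fixes the order: SHH first, SCD one week later.

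Section 9 handles fluid load in one sentence: "IDWG will be compared using paired and unpaired non-parametric testing", or a t-test if the variable is normally distributed. The outcome analyses name no covariate. For stunning, "Independent t-test will be used to compare the peak frequency of MS between SHH and SCD sessions". LVEF and segmental wall motion "will be compared using repeated measures and" a Bonferroni correction. The correlation list reads "Statistical correlations are planned for regional wall abnormalities, inflammatory indices, monocyte subsets and pre-dialysis blood pressures"; neither IDWG nor UF is on it.

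**The concern.** The comparison is within patient but not randomised in order. A factor that shifts between week one and week two, and is related to stunning, moves with the device. UF is such a candidate by the protocol's own account. It may also affect the measurement itself, since Section 8.4.1 calls wall motion and strain less, but not entirely, dependent on preload and afterload.

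A significance test on IDWG does not deal with this. It cannot establish balance with 10 patients, and it removes nothing from the effect estimate. IDWG is also only a proxy: it matches planned UF if dry weight was reached at the previous session, and net UF itself enters no analysis. At stake is whether a difference between sessions can be read as an SCD effect rather than partly an effect of fluid load.

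**Working it through.** **1. The plan's own figure.** Section 9 says "Sample size of 10 would appear to be sufficient to detect a difference of 20" percent, which "is based upon a standard deviation of 14%, significance level of 0.05 and 80% power". Two-sided, with 14% as the per-session SD: n = 2 × (1.96 + 0.84)² × 14² / 20² = 7.7, so 8 per session. The exact t calculation gives 9 (81.2% power), and 10 gives 85.5%. If 14% is instead the SD of the paired differences, the normal formula gives 3.85, so 4, and the exact paired t-test needs 7. Ten patients is consistent with the stated inputs on either reading. No UF term enters.

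**2. What a test of IDWG can show with n = 10** (two-sided 5%; each SD is that test's own).
- Paired t, imbalance 0.5 SD of the differences: noncentrality 0.5 × √10 = 1.58, 9 df, power 29%.
- Unpaired t, imbalance 0.5 SD: noncentrality 0.5 / √(2/10) = 1.12, 18 df, power 19%.
- Imbalance detectable with 80% power: 1.00 SD (paired), 1.32 SD (unpaired).

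**3. Scale of UF.** A gain of 0.04 kg/kg removed over 4 h is 0.04 × 1000 / 4 = 10 ml/h/kg. The cited 12.37 ml/h/kg is 12.37 × 4 / 1000 = 0.0495 kg/kg. The gap, 0.0095 kg/kg, is 0.57 to 0.85 kg at assumed weights of 60 to 90 kg. So a change of well under 1 kg between sessions spans the two UF figures that follow from the protocol.

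**4. Noise versus bias.** Write a patient's SCD minus SHH outcome difference as D = Δ + βU + e, where U is the within-patient UF difference. The mean of D is Δ + β × E(U).
- If E(U) = 0, the unadjusted paired estimate is unbiased. The variation from βU is already in the SD of D, so the paired interval keeps its coverage. Assuming a within-patient SD of weight gain of 0.5 to 1.0 kg and weights of 70 to 80 kg, the 95% range of the chance mean UF difference is ±1.96 × SD × √2 / √10 / (4 h × weight): ±1.4 ml/h/kg (0.5 kg, 80 kg) to ±3.1 ml/h/kg (1.0 kg, 70 kg). This is noise.
- If E(U) = m, not zero, the bias is β × m. The documents give neither β nor m.

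**5. Illustration only.** Assume no device effect, β of 2 to 4 points per ml/h/kg, SD of U 2 ml/h/kg and residual SD 12 points (20,000 simulated trials).

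| Mean UF difference | Bias, unadjusted | False-positive rate, unadjusted | False-positive rate, adjusted |
|---|---|---|---|
| 1 ml/h/kg | 2 to 4 points | 8% to 12% | about 5% |
| 2 ml/h/kg | 4 to 8 points | 15% to 35% | about 5% |

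**6. Cost of adjusting.** Let r be the correlation of U with D, and δ the true mean of U in SDs of U. The ratio of adjusted to unadjusted interval width (root mean square) is (t₈/t₉) × √[(1 − r²) × (1 + (1 + 10δ²)/7)], with t₈/t₉ = 2.306/2.262 = 1.019.
- δ = 0: +9% at r = 0, 0% at r = 0.4, −6% at r = 0.5, −22% at r = 0.7.
- δ = 0.5, r = 0: 1.019 × √1.5 = 1.25, so +25%.
- δ = 1, r = 0: 1.019 × √2.571 = 1.63; simulation gives +64%. At r = 0.7 it is still +17%.

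**The case against.** **Existing control.** Both sessions aim at the same dry weight, use the same 4 h UF window and flow rates (Section 4.1), and follow the patient's routine treatment day (Section 6.3.15) one week apart, which suggests the same weekday and interdialytic interval. This stands as partial control. It does not equalise the weight gain of the day, and no section requires equal UF.

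**Chance imbalance is not bias.** This stands in full (step 4). A reader might infer that any UF difference between sessions carries straight into the SCD estimate as bias. In a paired analysis only a systematic difference does, and the documents show neither its presence nor its size.

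**The unpaired test may have another purpose.** Section 9 does not name the groups for the IDWG comparison, and an unpaired test would be legitimate between different patients. However, Section 9 defines no such groups and says that patients are their own controls. The point is therefore confined to the between-session comparison.

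**There is no entry minimum of 10 ml/h/kg.** Correct. Section 5.1.8 admits patients prone to intradialytic hypotension with no weight-gain requirement, and the other route needs only some past sessions above 0.04 kg/kg. Step 3 gives a scale, not a floor.

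**Achieved UF is a poor covariate.** Correct. It is measured after treatment starts and may be altered by it, for example if hypotension limits fluid removal. Planned UF is fixed before treatment.

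**The trial is an exploratory pilot.** The synopsis calls the primary analyses descriptive. This limits the adjusted model to a supporting role. However, Section 9 also plans formal tests, so the handling of UF still matters.

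**Conclusion.** The point holds as a gap in the analysis plan that is cheap to close. Net UF is associated with stunning by the protocol's account, varies with the weight at each session, and is compared across an unrandomised fixed order. Section 9 only tests a proxy for it, with an option that ignores the pairing, and a paired test with 29% power for a 0.5 SD imbalance cannot show balance.

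Two things rest on inference or assumption. That UF is set separately at each session is inferred from Sections 6.3.4 and 6.3.15; no sentence says so directly. The figures in step 5 depend entirely on assumed slopes and imbalances. A reader might take them as the bias in this trial, or take UF as a proven cause of stunning. The documents support neither: Section 1 reports an association, and nothing states a systematic UF difference between the sessions.

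**What to change.** In Section 9:

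- Delete the unpaired option for the between-session IDWG comparison. Report the paired difference in IDWG and in planned net UF rate (pre-dialysis weight minus dry weight, over 4 h, in ml/h/kg), each with a 95% CI.
- Pre-specify a supportive analysis of the regional wall abnormality outcome: regress the within-patient SCD minus SHH difference on the within-patient difference in planned net UF. The intercept is the estimate at equal planned UF. Show it beside the unadjusted paired result. This presupposes that a paired result is planned; the independent t-test now named for stunning frequency does not supply one.
- Use achieved UF in a sensitivity analysis only. Take it from the weights before and after each session (Sections 8.3.1.9 and 8.3.1.36), because the citrate infusion of 400 ml/h (Section 6.3.4, Table 1) runs in the SCD session alone.

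The cost is some wording, one model and one degree of freedom, with no new data. The adjusted interval may be wider, and most so where the mean UF difference is large (step 6), which is why the unadjusted result stays beside it. The sample size need not change, because the adjusted model is supportive. Adjustment does not remove other confounding from the fixed order. No change to UF management is proposed.

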10.1 Definitions

An **Adverse Event** is any change from the Subject's baseline and usual (pre-treatment) condition, whether or not it is believed related to the experimental treatment. An adverse event, therefore, is any unfavorable and/or unintended sign, symptom, or disease that is temporally associated with the use of the experimental treatment and occurs for the first time after treatment initiation or, if present at the time of enrollment and treatment initiation, intensifies or indicates a worsened clinical condition..

Any Adverse Event, whether considered study-treatment related or not, which fits any of the criteria below, is considered a **Serious Adverse Event (SAE)**:

- ❖ Results in death.
- ❖ Is life-threatening (meaning that the Subject was at risk of death at the time of the event; this does not refer to an event which might have caused death if it had occurred in a more severe form).
- ❖ Requires inpatient hospitalization or prolongs the existing hospitalization.
- ❖ Is a persistent disability/incapacity.
- ❖ Is a congenital anomaly or birth defect.
- ❖ Is considered an important medical event by the Investigator (e.g., surgery, return to ICU, emergency procedures, etc.)

Medical judgment should be exercised in deciding whether other medical events may be considered serious. Important medical events which may not be immediately life threatening or result in death or hospitalization but which may jeopardize the Subject or require intervention to prevent one of the serious outcomes listed above should be considered serious.

Any Adverse Event, which is not consistent in specificity or severity with the current Investigator's Brochure including all amendments, is considered "**unexpected**".

Causality is defined as the probability that the adverse event may have been caused by the study treatment. The following definitions for causality assessment will be used in this study:

- ❖ **DEFINITELY RELATED:** A clinical event, including a significant change in a laboratory test, that occurs in a plausible time relationship to the study hemofiltration treatment, and which cannot be explained by concurrent disease or other drugs, chemicals, or procedures.

- ❖ **PROBABLY RELATED:** A clinical event, including a significant change in a laboratory test, occurring within a reasonable time sequence in relationship to the study hemofiltration treatment that is unlikely to be attributed to concurrent disease, other drugs, chemicals, or procedures, and that follows a clinically reasonable response upon withdrawal of the study hemofiltration treatment.
- ❖ **POSSIBLY RELATED:** A clinical event, including a significant change in a laboratory test, occurring within a reasonable time sequence in relationship to the study hemofiltration treatment that could also be explained by concurrent disease, drugs, chemicals, or procedures. The clinical course after withdrawal of the study hemofiltration treatment may be unclear with respect to the contribution of the study hemofiltration treatment to the adverse event.
- ❖ **DEFINITELY NOT:** An adverse event, including a significant change in a laboratory test, with a temporal relationship to the SCD treatment that makes an association with the study hemofiltration treatment improbable, and in which other drugs, procedures or underlying disease(s) provide likely explanation.

The **intensity** of all adverse events should be evaluated using the following definitions:

- ❖ **SEVERE:** An event requiring immediate intervention; causes significant discomfort
- ❖ **MODERATE:** An event that requires non-routine intervention; i.e., a new clinical treatment or diagnostic procedure, administered within an hour of the event; causes annoying discomfort
- ❖ **MILD:** An event that requires minimal clinical treatment, or an adverse event requiring monitoring but no intervention or treatment; causes slight discomfort

10.2 Reporting Requirements

All adverse events occurring from Time 0 through Day 14 must be recorded on the Adverse Event page of the Case Report Form (CRF).

Serious Adverse Events

In addition to recording data on the CRF, any SERIOUS adverse event (regardless of relationship to the study hemofiltration treatment) that occurs during the first study hemofiltration treatment will be reported to the IRB. The clinical site will be required to complete a written Serious Adverse Event report, which must be signed by the Sponsor-Investigator.

For any serious adverse event that is ongoing at the time of the initial report, periodic follow-up information will be required until the adverse event is resolved or is considered to be chronic and stable.

Sponsor Investigator Responsibilities

The Sponsor-Investigator will promptly review documented adverse effects and abnormal test findings to determine 1) if the abnormal test finding should be classified as an adverse effect; 2) if there is a reasonable possibility that the adverse effect was caused by the investigational device or, if applicable, other study treatment or diagnostic product(s); and 3) if the adverse effect meets the criteria for a serious adverse effect.

In accordance with 21 CFR Part 812.150(a)(1) and (b)(1), the sponsor shall promptly report the results of an evaluation of any serious and unanticipated adverse device effect to FDA, the University of Michigan IRBMED and participating investigators (if any) as soon as possible, but not later than 10 working days after the sponsor first receives notice of the effect. Thereafter, the sponsor shall submit such additional reports concerning the effect as the FDA requests. Complications and non-serious or anticipated adverse events should be documented and tabulated but need not be submitted by the sponsor to the FDA as individual reports.

Independent Data Review and Data and Safety Monitoring Committee

To protect the interests of research subjects and ensure that they are not exposed to undue risk, this trial will be monitored by an independent Data and Safety Monitoring Committee (DSMC). The DSMC will be appointed by the Sponsor-Investigator, and shall have no formal involvement with the subjects or the investigation and function independently of Sponsor-Investigator. The DSMC will be members independent from the sponsor-investigator and co-investigators. The DSMC will provide an independent, and unbiased assessments of adverse events and any need for study termination. The Committee will consist of one nephrologist and one cardiologist with expertise in heart failure and who are independent of the study team.

The DSMC will monitor the progress of the trial with a scheduled meeting or conference call. In addition to reviewing Serious Adverse Events (SAEs), the first DSMC meeting will focus on over all safety of the trial and study device and will make a determination as to whether or not the study should proceed.

The DSMC will also serve as the Clinical Events Committee (CEC), and will adjudicate all adverse events for clinical accuracy and relatedness to the treatment, and will also ensure a unified evaluation by applying standardized even criteria. The CEC will perform final adjudication of adverse events.

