4.3 Duration of Study

The total duration of participation will be approximately 3 weeks.

5. Subject Selection

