8.3.1 Study Treatment

Each Subject will have the treatments described below, during which identical study procedures will be performed during each study treatment.

Treatment 1: Initial standard hemodialysis treatment with heparin (SHH) anticoagulation.

Treatment 2: A single hemodialysis treatment with SCD treatment and regional citrate anticoagulation one week after Treatment 1.

Each subject's safety data will be monitored by the PI on an ongoing basis.

Prior to start of Study Treatment (SHH or SCD Treatment)

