8.3.1.40 Perform 2 D echo

8.3.1.41 Obtain blood for systemic soluble markers according to instructions in **Appendix 2**.

8.3.1.42 Obtain blood for flow cytometry according to instructions in **Appendix 2**.

Before Initiation of SCD Treatment

8.3.1.43 The PI must review all safety data of the Subject and determine their suitability to move to the SCD treatment. Further, the WBC count must be $>4000/\text{mm}^3$, neutrophil count >500 and platelet count $>50,000/\text{mm}^3$ in prior treatments.

Ionized calcium during SCD Treatment

8.3.1.44 The PI may draw more frequent iCa using i-STAT device if deemed necessary for safety concerns.

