Appendix 1. Schedule of Events

Event	4-week Screening Period	Hemodialysis (Procedures to be repeated on days study hemodialysis treatment(s) are given)							24 hour after (± 4 hours)
		Pre-Rx Baseline (time 0)	Rx start >0-<1h	1h	2h	3h	4h	5h	
Informed consent	X								
Review of entry criteria	X								
Echocardiogram ¹		X							X X
albumin		X							
Basic Metabolic Panel ⁶		X							X
CBC/diff/plt ⁶		X							X X
Pregnancy test ⁴	X								
Systemic soluble markers ²		X							X X
Leukocyte flow cytometry		X							X X
Physical examination		X							
Review/update medical history		X							
BP, HR, RR ⁵		X	X	X	X	X	X	X	X
Weight/temp		X							X
Concomitant medications	X	X	X	X	X	X	X	X	x
Adverse events		X	X	X	X	X	X	X	x
iCa ^{3,6}				X ⁷	X	X	X	X	
Visual inspection for hemolysis and clotting in blood circuit							X		

Notes:

1. Hemodialysis procedures should begin within 2 hours of completion of echocardiogram and completion of baseline procedures (physical examination, review/update medical history, vital signs (BP, HR, RR Weight/temp) and recording and review of concomitant medications.
2. Elastase, Hs CRP, IL-6, IL-10, IL-17, IL-23, G-CSF, TNF- α , MCP-1, IL-17, IL-23, IL-8, G-CSF, IL-1 β , Neopterin.
3. For SCD Treatment Protocol only, iCa will be drawn. Levels of iCa will be determined from extracorporeal circuit before citrate infusion site. Additional iCa may be obtained if clinically indicated and post SCD treatment session, upon PI's determination.
4. Pregnancy test: Quantitative bHCG test will be obtained in the screening period.
5. Vital signs (BP, HR, RR) would be recorded within 20 minutes of indicated times.
6. iCa, CBC/diff=plt, basic metabolic panel would be collected within 15 minutes of indicated times.
7. For SCD Treatment Protocol only, iCa will be drawn during this hour just prior to initiation of therapy, and within 10 minutes of starting therapy.

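### Adverse events must be recorded to Day 14, but nothing is scheduled beyond 24 hours after the SCD session, Day 14 has no stated starting point, and only the heparin week ends with a structured look-back

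*Combined protocol and SAP*

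**What the plan says.** Section 10.2 sets the recording window: "All adverse events occurring from Time 0 through Day 14 must be recorded on the Adverse Event page of the Case Report Form (CRF"). Adverse events are a key measurement and the first item under the primary analyses in the Synopsis, where the analysis is descriptive.

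The schedule does not reach that far. The last column of Appendix 1 is "24 hour after (± 4 hours"), and the procedures in Section 8.3.1 also stop at 24 hours after each session. Section 8.5 closes participation with a form and gives no day and no adverse-event enquiry: "A Study Termination form will be completed for all patients who have completed the Study Procedures according to the protocol".

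The starting point of the window is open. Appendix 1 labels its baseline column "Pre-Rx Baseline (time 0"), and that column belongs to a block headed "Procedures to be repeated on days study hemodialysis treatment(s) are given". Each patient therefore has two Time 0s.

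The order is fixed, heparin first. Treatment 2 is "A single hemodialysis treatment with SCD treatment and regional citrate anticoagulation one week after Treatment 1". Its baseline repeats the adverse-event check, history update, physical examination and CBC. Item 8.3.1.43 adds a review before the SCD session: "The PI must review all safety data of the Subject and determine their suitability to move to the SCD treatment". Neither the schedule nor the text has a matching step a week after the SCD.

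**The concern.** A recording window is only as good as the contacts that fill it. The plan asks for events to Day 14, but after the SCD session it schedules no one to ask about them beyond the first day. The heparin week, by contrast, ends with a planned history, examination, blood count and investigator review. The session with the investigational device thus has the weaker ascertainment of late events.

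This matters for three reasons:

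- Section 3 names safety as part of the objective, and each patient is his or her own control, so a table of events by session is a natural product of the trial.
- The Background reports effects that outlast a day: a monocyte shift lasting as long as two weeks in a subset of seven diabetic patients, and improved cardiac function up to four weeks in dogs. These are not harms, but they show that the protocol does not regard the device's action as over at 24 hours.
- The safety committee adjudicates adverse events, but it can adjudicate only those that have been recorded.

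The undefined Time 0 is a problem in its own right. Staff could stop recording 7 days after the SCD or 14 days after it, and either would comply with Section 10.2.

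**Working it through.** **1. Is a later visit planned elsewhere?** Appendix 2 gives volumes per draw and in total, which fixes the number of draws.

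- CBC: 18/3 = 6. Soluble markers: 66/11 = 6. Flow cytometry: 6/1 = 6. Each equals 3 time points in Appendix 1 (baseline, 5 h, 24 h) × 2 sessions.
- Basic metabolic panel: 8/2 = 4, which is baseline and 5 h × 2 sessions.
- Ionized calcium: 3/0.5 = 6, all in the SCD session.

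These totals reproduce the Appendix 1 schedule and leave no draw for a visit after 24 hours. (Albumin gives 1/1 = 1 draw where Appendix 1 implies 2. That mismatch does not bear on later visits.)

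**2. Days without a scheduled enquiry.** Put heparin on Day 0 and the SCD on Day 7, and count the 24-hour check as covering 1 day.

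- Heparin, Days 0 to 7: closed by the Treatment 2 baseline and the investigator review, so 0 of 7 days are left open.
- SCD, Day 14 counted from heparin: window 14 − 7 = 7 days, uncovered 7 − 1 = 6 days (86%).
- SCD, Day 14 counted from the SCD: window 14 days, uncovered 14 − 1 = 13 days (93%).

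Adding the 5-hour session to the 24 hours gives 29 h, or 1.2 days. The uncovered time is then 5.8 of 7 days (83%) or 12.8 of 14 days (91%). The conclusion is the same.

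**3. Effect on recorded events.** Assume an equal and constant true rate after both sessions, complete capture where a scheduled check closes the period, and a share p of events captured where none does. The documents give no value for p, so the whole range is shown. The heparin period is taken as the 7 days before the SCD.

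- Day 14 from heparin: recorded SCD/heparin ratio = (1 + 6p)/7. Both windows are 7 days, so this is also the per-day ratio.
- Day 14 from the SCD, raw counts: (1 + 13p)/7.
- Day 14 from the SCD, per day of window: (1 + 13p)/14.

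| p | From heparin | From SCD, raw | From SCD, per day |
|---|---|---|---|
| 0 | 0.14 | 0.14 | 0.07 |
| 0.25 | 0.36 | 0.61 | 0.30 |
| 0.50 | 0.57 | 1.07 | 0.54 |
| 0.75 | 0.79 | 1.54 | 0.77 |
| 1 | 1.00 | 2.00 | 1.00 |

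On the second anchor, raw counts break even at 1 + 13p = 7, so p = 6/13 = 46%. Below that the SCD has fewer recorded events; above it, more, because its window is twice as long. Per day of window the ratio is below 1 for every p below 1 on either anchor.

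**The case against.** Passive capture will not be zero. Section 10.2 makes recording mandatory whether or not there is a visit. Patients dialyse three times a week, and Section 6.3.2 describes them as already dialysing in the university's unit. The Synopsis promises a safety analysis by the investigator before each patient's next hemodialysis, Section 8.3.1 promises ongoing monitoring, and an independent committee adjudicates events. Most of the named risks (circuit clotting, air entry, hypocalcaemia, ischaemic arrhythmia) arise during dialysis, where both sessions are observed alike. All of this stands, and it argues for a p well above 0. But none of these provisions names a day, a contact or an adverse-event question, and none clearly reaches Day 14. It is also not stated whether the next hemodialysis means the next study session or the next routine one.

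Three stronger readings are tempting, and the documents do not support them:

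- A reader might infer that the trial's safety comparison is biased in favour of the SCD. No between-session comparison of adverse events is specified, and the direction in raw counts is settled only if Day 14 runs from heparin.
- A reader might take the stated participation ("The total duration of participation will be approximately 3 weeks") as proof that Day 14 runs from each session, since 7 + 14 = 21 days. Screening also takes time, and 14 days plus about a week of screening fits equally well.
- A reader might multiply up to an expected count, for example 7 events against 1.2 in 10 patients at 0.1 events per patient-day. That needs a rate the documents do not give, and p = 0.

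**Conclusion.** The point holds as a gap in ascertainment and an undefined window. Read as written, the plan leaves about 6 of 7 or 13 of 14 post-SCD days without a scheduled adverse-event enquiry, while the heparin week has a full look-back. Late events after the SCD are therefore probably under-counted per day of window. The size depends on p, which is unknown: with Day 14 counted from heparin, the recorded ratio runs from 0.14 to 1.00 under equal true rates. These ratios also rest on a constant rate and on the Day 7 look-back finding every heparin-week event. If it misses some, the imbalance is smaller.

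This should be fixed, but it does not invalidate a 10-patient exploratory pilot with descriptive safety reporting. It is a cheap improvement.

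**What to change.** 1. In Section 10.2, state which session anchors Time 0 and Day 14. Do this openly, and do not shorten the window that Section 10.2 now sets.
2. Add to Appendix 1 a review of adverse events, concomitant medications and medical history 7 days after the SCD, at a routine dialysis session or by phone, with the same questions as at the Treatment 2 baseline. If Day 14 counts from the SCD, add a second review on that day.
3. In Section 8.5, complete the Study Termination form only after the last of these contacts.
4. If adverse events are tabulated by session, use equal 7-day windows: start of Treatment 1 to start of Treatment 2, and start of Treatment 2 to 7 days after it. List later events separately, so that none is counted under both sessions.

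The cost is protocol wording and one or two short reviews in each of 10 patients, with no extra test or staff. The downside is that slightly more SCD-period events will be recorded.
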